3.2. Final Analyses

The final planned primary analyses will be performed after the completion of the following sequential steps:

1. All participants have completed the study as defined in the protocol
2. All required database cleaning activities have been completed and final database release and database freeze has been declared by Data Management.

4. ANALYSIS POPULATIONS

Population	Definition / Criteria	Analyses Evaluated
Safety	
 Consists of all subjects who receive at least 1 dose of study drug and have at least one postdose safety assessment. 	
 Study Population Safety
PK Population	
 Consists of all subjects who received at least 1 dose of gepotidacin and have evaluable PK data for gepotidacin. A subject is considered to have evaluable PK data for gepotidacin if the subject has at least 1 measurable post-dose PK concentration value for gepotidacin that was not excluded from the analysis due to a protocol deviation. 	
 PK Concentration
PK Parameter	
 Consist of all subjects in the PK Population, for whom valid and evaluable PK parameters were derived. This population will be used in the assessment and characterization of PK parameters. 	
 PK parameter PK statistical analysis

NOTES:

- Please refer to [Appendix 8](#): List of Data Displays which details the population to be used for each display being generated.

4.1. Protocol Deviations

Important protocol deviations (including deviations related to study inclusion/exclusion criteria, conduct of the trial, patient management or patient assessment) will be summarized and listed.

Protocol deviations will be tracked by the study team throughout the conduct of the study in accordance with the Protocol Deviation Management Plan.

- Data will be reviewed prior to freezing the database to ensure all important deviations and deviations which may lead to exclusion from the analysis are captured and categorized on the protocol deviations dataset.
- This dataset will be the basis for the summaries and listings of protocol deviations.

A separate summary and listing of all inclusion/exclusion criteria deviations will also be provided. This summary will be based on data as recorded on the inclusion/exclusion page of the electronic case report form (eCRF).

5. CONSIDERATIONS FOR DATA ANALYSES AND DATA HANDLING CONVENTIONS

5.1. Study Treatment & Sub-group Display Descriptors

Treatment Group Descriptions ^[1]				
Study Part	Hepatic Impairment Group		Data Displays for Reporting	
	Code	Description	Description	Order ^[2]
1, 2	D, E ^[3]	Normal Hepatic Function	Normal	1
1	B	Moderate Hepatic Impairment	Moderate	3
2	A ^[4]	Mild Hepatic Impairment (optional)	Mild	2
2	C ^[5]	Severe Hepatic Impairment	Severe	4

NOTES:

1. Only groups that are present in the data will actually be presented.
2. Order represents treatments being presented in TFL, as appropriate.
3. Based on emergent data from Part 1, matching participants with normal hepatic function in Part 2 (Group E) may be enrolled (e.g., if a change in dose is needed or if the demographic data of the mild and/or severe hepatic impairment groups is not well matched to the moderate control data [Group D]). If there is no change in dose, then these two groups will be combined for presentation in the outputs.
4. Based on emergent data from Part 1, participants with mild hepatic impairment (Group A) may not be enrolled in Part 2 if there is not a significant difference between participants with moderate hepatic impairment and participants with normal hepatic function.
5. If AUC and/or C_{max} are predicted to exceed the threshold, the dose may be adjusted for participants with severe hepatic impairment (Group C). Due to the potential difficulty in identifying eligible participants with severe hepatic impairment, the sponsor may stop the study prior to full enrollment in Part 2 provided that a minimum of 6 evaluable participants with severe hepatic impairment have been enrolled.

5.2. Baseline Definitions

For all endpoints (except as noted in baseline definitions) the baseline value will be the last available assessment prior to time of study drug administration, unless noted otherwise.

Parameter	Study Assessments Considered as Baseline			Baseline Used in Data Display
	Screening	Day -1	Day 1 (Pre-Dose)	
Safety				
Hematology	X	X		Day -1
Clinical Chemistry	X	X		Day -1
12-Lead ECG	X	X	X	Day 1 (Pre-Dose)
Vital Signs	X	X	X	Day 1 (Pre-Dose)

NOTES:

- Unless otherwise stated, the mean of replicate assessments at any given time point will be used as the value for that time point.

Unless otherwise stated, if baseline data is missing no derivation will be performed and baseline will be set to missing.

5.3. Other Considerations for Data Analyses and Data Handling Conventions

Other considerations for data analyses and data handling conventions are outlined in the appendices:

Section	Component
10.2	Appendix 2 : Study Phases and Treatment Emergent Adverse Events
10.3	Appendix 3 : Data Display Standards & Handling Conventions
10.4	Appendix 4 : Derived and Transformed Data
10.5	Appendix 5 : Reporting Standards for Missing Data
10.6	Appendix 6 : Values of Potential Clinical Importance

6. STUDY POPULATION ANALYSES

6.1. Overview of Planned Study Population Analyses

The study population analyses will be based on the Safety population, unless otherwise specified.

Study population analyses including analyses of subject's disposition, protocol deviations, demographic and baseline characteristics, prior and concomitant medications, and exposure and treatment compliance will be based on GSK Core Data Standards. Details of the planned displays are presented in [Appendix 8: List of Data Displays](#).

7. PHARMACOKINETIC ANALYSES

7.1. Primary Pharmacokinetic Analyses

7.1.1. Endpoint / Variables

7.1.1.1. Drug Concentration Measures

Refer to [Appendix 3](#): Data Display Standards & Handling Conventions (Section [10.3.3](#) Reporting Standards for Pharmacokinetic). Only total gepotidacin plasma PK concentrations will be measured and reported. Therefore, unbound plasma PK concentrations will be derived by multiplying the total plasma PK concentrations by 0.67, to correct for the low plasma protein binding of gepotidacin (33%) observed in previous studies.

7.1.1.2. Derived Pharmacokinetic Parameters

Pharmacokinetic parameters will be calculated by standard non-compartmental analysis according to current working practices and using the currently supported version of WinNonlin. All calculations of non-compartmental parameters will be based on actual sampling times. Pharmacokinetic parameters listed will be determined from the plasma concentration-time data, as data permits.

Parameter	Parameter Description
AUC(0-∞)	Area under the concentration-time curve from time 0 (predose) extrapolated to infinite time, calculated as: $AUC = AUC(0-t) + C(t) / \lambda z$ where C(t) is the last quantifiable concentration
Cmax	Maximum observed concentration, determined directly from the concentration-time data

NOTES:

- Additional parameters may be included as required.
- For the derivation of unbound plasma PK parameters; the total plasma PK parameters AUC(0-∞), and Cmax will be multiplied by 0.67, to correct for the low plasma protein binding of gepotidacin (33%) observed in previous studies.

7.1.2. Summary Measure

Area under concentration-time curve (AUC[0-∞]) and Cmax following single doses of gepotidacin in subjects with normal hepatic function and hepatically impaired subjects.

7.1.3. Population of Interest

The primary pharmacokinetic analyses will be based on the PK population for plasma PK concentrations and the PK parameter population for plasma PK parameters and statistical analysis, unless otherwise specified.

7.1.4. Statistical Analyses / Methods

Details of the planned displays are provided in [Appendix 8](#): List of Data Displays and will be based on GSK Data Standards and statistical principles.

Unless otherwise specified, endpoints/variables defined in Section 7.1.1 will be summarized using descriptive statistics, graphically presented (where appropriate) and listed.

7.1.4.1. Statistical Methodology Specification

The following pharmacokinetic statistical analyses will only be performed if sufficient data is available (i.e. if participants have well defined plasma profiles).

Endpoint / Variables

 Plasma primary pharmacokinetic (PK) endpoints include AUC(0-∞) and Cmax of gepotidacin, as data permit.
Model Specification

 The plasma ln-transformed AUC(0-∞) and Cmax values for gepotidacin in the hepatic impairment groups and the normal hepatic function group will be compared using an analysis of variance (ANOVA).
Model Checking & Diagnostics

 Model assumptions will be applied, but appropriate adjustments may be made based on the data.
Model Results Presentation

 Statistical analysis by ANOVA will be presented in tabular format with geometric mean ratios between hepatic impairment groups and normal hepatic function group, and 90% CIs for the ratios of AUC(0-∞) and Cmax for gepotidacin.

7.2. Secondary Pharmacokinetic Analyses

7.2.1. Endpoint / Variables

7.2.1.1. Drug Concentration Measures

Refer to [Appendix 3: Data Display Standards & Handling Conventions \(Section 10.3.3 Reporting Standards for Pharmacokinetic\)](#)

7.2.1.2. Derived Pharmacokinetic Parameters

Pharmacokinetic parameters will be calculated by standard non-compartmental analysis according to current working practices and using the currently supported version of WinNonlin. All calculations of non-compartmental parameters will be based on actual sampling times.

Plasma pharmacokinetic parameters listed below will be determined from the total plasma concentration-time data, as data permits.

Parameter	Parameter Description
AUC(0-t)	Area under the concentration-time curve from time 0 (predose) to time of last quantifiable concentration, to be calculated using the linear trapezoidal rule for each incremental trapezoid and the log trapezoidal rule for each decremental trapezoid
Tmax	Time to first occurrence of Cmax
tlag	Lag time before observation of drug concentrations in sampled matrix
t _{1/2}	Terminal half-life will be calculated as: $t_{1/2} = \ln 2 / \lambda_z$
λ_z	Terminal-phase rate constant
CL/F	The apparent oral clearance, calculated as: $CL/F = \text{Dose} / AUC(0-\infty)$
Vz/F	The apparent volume of distribution during the terminal phase, calculated as: $V_z/F = CL / \lambda_z$

NOTES:

- Additional parameters may be included as required.
- For the derivation of unbound plasma PK parameters; the total plasma PK parameters AUC(0-t) will be multiplied by 0.67, and the total plasma PK parameter CL/F will be divided by 0.67, to correct for the low plasma protein binding of gepotidacin (33%) observed in previous studies.

Pharmacokinetic parameters listed will be determined from the urine concentration-time data, as data permits.

Parameter	Parameter Description
Ae total	Total unchanged drug (total amount of drug excreted in urine), calculated by adding all the fractions of drug collected over all the allotted time intervals
Ae(t1-t2)	Amount of drug excreted in urine in time intervals for predose, 0 to 6, 6 to 12, 12 to 24, 24 to 36, and 36 to 48 hours after dosing for subjects with hepatic impairment; and predose, 0 to 2 hours, 2 to 4 hours, 4 to 6 hours, 6 to 8 hours, 8 to 12 hours, 12 to 24 hours, 24 to 36 hours, and 36 to 48 hours for subjects with normal hepatic function; calculated by multiplication of the urine concentration for a time interval and the length of this time interval.
AUC(0-t)	Area under the urine concentration-time curve over t hours where t = 12, 24, and 48 hours. The AUC(0-t) will be calculated by the linear trapezoidal rule based on the urine concentration data from each collection interval versus the corresponding urine collection interval.
Fe%	Percentage of the given dose of drug excreted in urine, calculated as: $fe\% = (Ae \text{ total}/\text{Dose}) \times 100$
CLr	Renal clearance of drug, calculated as: $CLr = Ae \text{ total}/AUC(0-t)$ where AUC(0-t) is the area under the plasma concentration-time curve over all the allotted time intervals of urine collections.

NOTES:

- Additional parameters may be included as required.

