10.3. Statistical Analyses

10.3.1. Pharmacokinetic Analyses

Plasma and urine concentrations of gepotidacin will be subjected to PK analyses using noncompartmental methods. Based on the individual concentration time data the following parameters will be estimated:

Plasma:

AUC(0-∞)	Area under the concentration-time curve from time 0 (predose) extrapolated to infinite time
AUC(0-t)	Area under the concentration-time curve from time 0 (predose) to time of last quantifiable concentration
Cmax	Maximum observed concentration
λ_z	Terminal-phase rate constant
t _{1/2}	Terminal phase half life
Tmax	Time to first occurrence of Cmax
t _{lag}	Lag time
CL/F	Apparent oral clearance

V_z/F Apparent volume of distribution

Urine:

Ae total Total unchanged drug (total amount of drug excreted in urine), calculated by adding all the fractions of drug collected over all the allotted time intervals

Ae(t1-t2) Amount of drug excreted in urine in a time intervals for predose, 0 to 6, 6 to 12, 12 to 24, or 24 to 36, and 36 to 48 hours after dosing for participants with hepatic impairment; and predose, 0 to 2 hours, 2 to 4 hours, 4 to 6 hours, 6 to 8 hours, 8 to 12 hours, 12 to 24 hours, 24 to 36 hours, and 36 to 48 hours for participants with normal hepatic function

fe% Percentage of the given dose of drug excreted in urine, calculated as:

$$fe\% = (Ae \text{ total}/Dose) \times 100$$

CL_r Renal clearance of drug, calculated as: $Ae \text{ total}/AUC(0-t)$

AUC(0-12) Area under the concentration-time curve from time 0 (predose) to 12 hours

AUC(0-24) Area under the concentration-time curve from time 0 (predose) to 24 hours

AUC(0-48) Area under the concentration-time curve from time 0 (predose) to 48 hours

Plasma concentrations and urine concentrations of gepotidacin and the associated PK parameters will be listed, and summary statistics (n, mean, median, standard deviation [SD], minimum, maximum, and coefficient of variation [CV]) will be presented by day and treatment. Mean and individual plasma concentration versus time profiles will be presented graphically on linear and semilogarithmic scales.

The natural log-transformed plasma AUC(0-∞) and C_{max} values for gepotidacin in the hepatic impairment groups and normal hepatic function groups will be compared using an analysis of variance. Geometric mean ratios between hepatic impairment groups and normal hepatic function groups, and 90% CIs for the ratios of AUC(0-∞) and C_{max} for gepotidacin will be presented.

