2.2. Study Objective(s) and Endpoint(s)

Objectives	Endpoints
Primary Objectives	Primary Endpoints

 To compare the plasma PK parameters of a 1500 mg oral dose of gepotidacin in normal healthy participants to participants with mild, moderate, and severe hepatic impairment 	
 Plasma gepotidacin AUC(0-∞) and Cmax, as data permit.
Secondary Objectives	Secondary Endpoints

 To assess the safety and tolerability of gepotidacin administered as a 1500 mg oral dose in normal healthy participants compared with participants with mild, moderate, and severe hepatic impairment To compare the secondary plasma PK parameters of 1500 mg oral dose of gepotidacin in normal healthy participants with participants with mild, moderate, and severe hepatic impairment To compare the urine PK parameters of a 1500 mg oral dose of gepotidacin in normal healthy participants with participants with 	
 12-lead safety ECG readings, change from baseline in vital sign measurements (blood pressure and heart rate), monitoring of AEs, toxicity grading of clinical laboratory test results, and physical examinations Plasma gepotidacin AUC(0-t), Tmax, tlag, CL/F, Vz/F, λz, and t1/2, as data permit Urine gepotidacin PK endpoints: 
 Primary: Ae total, fe %, and CLr, as data permit Secondary: Ae(t1-t2), AUC(0-12), AUC(0-24), and AUC(0-48), as data permit

Objectives	Endpoints
mild, moderate, and severe hepatic impairment	
Exploratory Objectives	Exploratory Endpoints

• To evaluate the saliva PK parameters of a 1500 mg oral dose of gepotidacin in normal healthy participants compared with participants with mild, moderate, and severe hepatic impairment	
• Saliva gepotidacin PK endpoints:
○ Primary: AUC(0-∞) and Cmax, as data permit○ Secondary: AUC(0-t), Tmax, λz, t1/2, CL/F, Vz/F, and saliva to unbound plasma AUC(0-t) and AUC(0-∞) ratios (RAUC) of gepotidacin, as data permit.

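### The SAP derives the amount excreted in urine as concentration times hours rather than concentration times volume, which misdefines Ae, fe% and CLr

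*SAP*

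**What the plan says.** The urine table in SAP 7.2.1.2 names Ae(t1-t2) as an amount of drug, then gives the rule for computing it: "calculated by multiplication of the urine concentration for a time interval and the length of this time interval". Three other parameters in the SAP rest on that line or sit beside it:

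- Ae total is the sum of the interval values, "calculated by adding all the fractions of drug collected over all the allotted time intervals".
- fe% is Ae total divided by dose, times 100. CLr is Ae total divided by AUC(0-t), "where AUC(0-t) is the area under the plasma concentration-time curve over all the allotted time intervals of urine collections".
- Urine AUC is a separate parameter with its own rule: "The AUC(0-t) will be calculated by the linear trapezoidal rule based on the urine concentration data from each collection interval".

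SAP 2.2 lists the urine endpoints as "Primary: Ae total, fe %, and CLr, as data permit", under a secondary objective. SAP 7.2.4.1 and Table 3.8 plan an ANOVA of untransformed CLr, with a least squares mean difference and 90% CI. The only other urine parameter analysed this way is AUC(0-48). Table 3.8 is due at the Part 1 interim as well as at the final analysis.

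Protocol 10.3.1 defines the interval parameter only as "Amount of drug excreted in urine in a time intervals for predose" and the later intervals, with no formula for it. The table of changes from the protocol in SAP 2.1 does not mention the urine derivation.

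**The concern.** An excreted amount is the drug concentration in the collected urine multiplied by the volume of that urine. The SAP replaces volume with elapsed time. The result is a rectangle-rule version of the urine AUC that the plan already derives by the trapezoidal rule. The urine analysis then contains two concentration-by-time measures and no mass.

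The consequence goes beyond units. For the same amount of drug excreted, more urine means a lower concentration, so the SAP quantity falls as urine flow rises. A group that passes more urine would appear to have lower renal clearance even if the kidneys handle the drug identically. Hepatically impaired participants may differ from controls in this respect; the Child-Pugh table in Protocol 7.3, for example, allows for medication to control ascites. The documents give no urine-flow data, so neither the direction nor the size of any such bias is known in advance. As written, the plan cannot answer the urine objective for Ae total, fe% and CLr.

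**Working it through.** The plan states no result for these parameters, so there is no figure of its own to reproduce. The check is a unit analysis followed by an illustration.

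**Inputs from the documents.** Dose 1500 mg. About 20% of an oral dose recovered in urine as parent drug (Protocol 3.1). Plasma AUC of 48 µg·h/mL, the study's threshold, used here only as a convenient denominator. Urine collection intervals of 0–6, 6–12, 12–24, 24–36 and 36–48 h for impaired participants, and 0–2, 2–4, 4–6, 6–8, 8–12, 12–24, 24–36 and 36–48 h for controls.

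**Assumption.** Urine flow is not in the documents. I take 62.5 mL/h, range 42 to 83, constant over 48 h unless stated.

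**Step 1: units.**
- Mass rule: Ae = C × V, so (µg/mL) × mL = µg.
- SAP rule: C × Δt, so (µg/mL) × h = µg·h/mL.
- SAP fe%: (µg·h/mL)/mg, which is not a percentage.
- SAP CLr: (µg·h/mL)/(µg·h/mL), which has no unit and is not a clearance.

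This step needs no assumption.

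**Step 2: how the two rules differ.** Let A be the true amount in an interval and Q = V/Δt the urine flow. Then C = A/V, and the SAP term is C × Δt = A/Q. Summed over intervals, the SAP's Ae total is ΣA/Q. With constant flow this is (total excreted)/Q.

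**Step 3: size.** Total excreted is 0.20 × 1500 mg = 300 mg = 300,000 µg.

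| Flow (mL/h) | SAP Ae total = 300,000/flow (µg·h/mL) | SAP fe% (number only) = Ae total/1500 × 100 | SAP CLr (no unit) = Ae total/48 |
|---|---|---|---|
| 42 | 7,143 | 476 | 149 |
| 62.5 | 4,800 | 320 | 100 |
| 83 | 3,614 | 241 | 75 |

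The volume rule gives the same answer at every flow: Ae total 300 mg, fe% 20, and CLr = 300 mg/48 mg·h/L = 6.25 L/h.

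**Step 4: between-group effect of flow.** Suppose true CLr is identical and flow is 1.5 times higher in one group. The apparent ratio is 1/1.5 = 0.67. On the difference scale that the SAP uses, flows of 62.5 and 93.75 mL/h give 100 and 300,000/93.75/48 = 66.7. The difference is −33.3 where the true difference is zero.

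**Step 5: effect of the different collection schedules.** Give both groups the same excretion (assumed half-life 8 h, 300 mg over 48 h) and the same varying flow (assumed 150, 90 and 30 mL/h over 0–2, 2–4 and 4–6 h, then 60 mL/h).

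- The amounts in those first three intervals are about 48,490, 40,770 and 34,290 µg, total 123,550 µg. The remaining 176,450 µg is excreted at 60 mL/h.
- Controls (three short intervals): 48,490/150 + 40,770/90 + 34,290/30 ≈ 1,919. Adding 176,450/60 ≈ 2,941 gives 4,860.
- Impaired (one 0–6 h interval, mean flow 90 mL/h): 123,550/90 ≈ 1,373. Adding 2,941 gives 4,314.
- Ratio 4,314/4,860 = 0.89, where the truth is 1.00.

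In this example the SAP rule creates a group difference from the collection schedule alone. The volume rule returns 300 mg for both groups.

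**The case against.** The strongest reply is that this is a slip of wording. The same table calls the parameter an amount and describes Ae total as "Total unchanged drug (total amount of drug excreted in urine), calculated by adding all the fractions of drug collected", fe% is described as a percentage of the dose, and the section invokes standard non-compartmental analysis in WinNonlin. The program may well use volume. A literal fe% in the hundreds would be noticed, and Ae could be recalculated if volumes were recorded. Protocol 9.5.2 names only the date and time of urine collection but leaves processing details to the Study Reference Manual, so its silence on volume does not show that volume goes unrecorded.

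Much of this is fair. The documents do not show that the reported results will be wrong, only that they will be if the SAP is followed. But a general reference to standard practice does not override a specific contrary formula beside it, and neither document gives a volume-based rule anywhere. A programmer working from the SAP, or a checker validating against it, would be working to the wrong definition.

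Three limits on the illustration also stand. The tabulated values and the 0.67 need constant flow. CLr is compared as a difference, not a ratio. The rectangle sum resembles the urine AUC(0-48) but is not identical to it. None of these affects the unit error.

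**Conclusion.** The concern holds. As written, SAP 7.2.1.2 does not produce an amount, and Ae(t1-t2), Ae total, fe% and CLr are all misdefined. The unit error is certain. The size depends on urine flow: under the assumed 42 to 83 mL/h, true excretion of 300 mg becomes about 7,140 to 3,610 µg·h/mL, and a 1.5-fold flow difference turns equal clearances into an apparent ratio of 0.67.

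The scope is limited. These endpoints serve a secondary objective, and of the four only CLr is formally compared. Plasma AUC(0-∞) and Cmax, urine AUC(0-48), and the mean AUC and Cmax thresholds applied after Part 1 are unaffected. The protocol does not share the error: its fe% definition, "Percentage of the given dose of drug excreted in urine, calculated as" Ae total over dose, is sound once Ae total is a mass. The point should still be corrected before any analysis, because a formally analysed endpoint is defined by the wrong formula.

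**What to change.** In SAP 7.2.1.2, define Ae(t1-t2) as the urine concentration in the interval multiplied by the urine volume collected in that interval, and Ae total as the sum of these over 0 to 48 h. Leave the fe% and CLr formulas as they are.

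Confirm that total urine volume per interval (or weight, with a stated conversion) is a recorded field, and say so in the SAP. This check is urgent: if volume is not recorded at collection, Ae, fe% and CLr cannot be recovered later. Also confirm that the programmed derivation used for the Part 1 interim follows the corrected definition.

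The cost is one line of SAP text and a check of the data fields. If volume is already captured, no extra participants, samples or procedures are needed.
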